#### 4. Study design

#### 4.1. Primary outcomes

#### 4.1.1 Primary outcome measure and endpoint

The primary fMRI outcome will be change in amygdala BOLD response to emotional faces from baseline (prep, 1 day pre-DD1) to scan 2 at 6-weeks post-DD1. Change after psilocybin (condition 1) vs change after escitalopram (condition 2).

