## 1.1. Basic study design

The main experimental condition (**condition 1**) in this study will involve two high doses of 25mg psilocybin (per os, p.o.), 3 weeks apart. The first dose will be followed by 6 weeks of daily (inert) placebo capsule ingestion (condition 1, fig. 1). The control condition (**condition 2**) will involve two dosing sessions, also 3 weeks apart, with a presumed inactive dose of

psilocybin (1mg p.o.). The first dose will be followed by 6-weeks of daily escitalopram capsule ingestion (fig. 1).

Thus, there will be a dedicated on-site dosing day for both conditions (named here 'initial dosing session') followed by 6 weeks of daily capsule ingestion at home and a second dosing session 3 weeks after the first. The primary endpoint for assessing efficacy is 6 weeks after the initial dosing session, when the blind will be broken at the final study visit. Unblinded follow-up will occur for a further 6 months to assess safety and any potential enduring effects.

The main purpose of this design is to test the hypothesis that two doses of psilocybin, a design similar to what may be done in future therapy, will show a superior efficacy to escitalopram and crucially, a different *mechanism of action*. Secondarily, we predict that conditions 1 and 2 will show comparable efficacy at 6 weeks but with a different side-effect profile, e.g. we predict that changes in sexual dysfunction will be different across conditions and that psilocybin will act more rapidly to alleviate depressive symptoms.

Regarding the primary outcome, we will use functional magnetic resonance imaging (fMRI) at baseline and six weeks after the initial dosing session to identify how brain activity changes before and after two doses of 25mg psilocybin vs 6 weeks of daily escitalopram.

We predict that fMRI measured amygdala blood oxygen level dependent (BOLD) responses to emotional faces after-versus-before treatment will be greater in condition 1 (psilocybin) than in condition 2 (escitalopram).

This trial promises to significantly advance our knowledge of the safety, efficacy and mechanism of action of psilocybin for MDD by comparing it with a major conventional treatment for depression. The comparison with escitalopram adds an important component to this trial which may ultimately lead to the development of psilocybin as an alternative treatment option for patients with MDD.

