#### 2.3.3. Recruitment strategy

To minimise/address pre-study biases, recruitment will predominantly be via referrals (we have good links with Clinical Research Networks (CRNs), Improving Access to Psychological Therapies (IAPT), local clinics and clinicians) and Clinical Record Interactive Search systems (CRIS Health Ltd). A Facebook page has also been created for the trial in order to aid recruitment, which will be managed by the team: https://www.facebook.com/Psilodep-RCT-334207224132116/. Prior attitudes to treatments will be collected at baseline and entered into regression analyses. Patients will be randomly allocated to one of the two conditions after eligibility is confirmed post screening. We will endeavour to recruit patients who are currently unmedicated for their depression. Where patients are medicated, withdrawal from antidepressants would be required prior to participation and this process would be done with adequate washout and appropriate titration and carefully monitored in collaboration with the patient and their primary care giver

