#### 4.2. Volunteers

#### 4.2.1. Sample size

A baseline versus 5-weeks post-treatment reduction of -9.2 (SD = 5.6) on the QIDS was observed in our recent pilot study. To inform what can be expected with 1mg psilocybin, we can refer to the recent end-of-life anxiety trial of Griffiths et al. [66] in which the reduction in scores on another standard scale (BDI) seen with the control condition (1-3mg/ 70kg psilocybin) was 50% that of the active condition, i.e. a reduction of 10.7 (22-30mg/70kg, active) versus 5.5 (1-3mg/70kg, control) at 5-weeks post-treatment. If 1mg psilocybin is equally as effective as the 1-3mg/70kg in the Griffiths study, i.e. 50% of the active dose (which is a conservative prediction, given that the difference in doses is greater, and the time since treatment is shorter), we can expect a mean reduction in QIDS scores of 9.2/2 = 4.7 points for

the 1mg condition. If we assume equal variance for both conditions, we would require 20 patients per condition to achieve the desired power of 80%, p < 0.05. We therefore propose to recruit a minimum of 30 patients per condition (60 completers in total for the RCT). These are appropriate numbers for the imaging, given that significant baseline v one-day post-treatment effects are being observed in BOLD resting-state functional connectivity, amygdala activations to emotional faces and CBF with just 15 patients in my recent pilot study (papers in preparation). Significant fMRI findings have been reported with escitalopram in similar paradigms and with similar sample sizes [67]. Equivalent efficacy (primary outcome) is predicted for the escitalopram vs 25mg psilocybin conditions but with different mechanisms of action. For example, we predict greater improvements in wellbeing (WEMWBS) with 25mg psilocybin vs escitalopram at 6-weeks post dosing day 1.

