## 10. Analysis

The data collected from this study will be used to gather new information and inform future studies. Data will be tabulated and descriptive parameters derived. The study is powered for a baseline vs week 6 t-test on the QIDS-16 (condition 1 vs condition 2) and this is the primary efficacy outcome and endpoint.

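### Section 4.1.1 states the primary fMRI contrast as change versus change and names no baseline adjustment; analysed that way it is valid but less precise than it could be at no extra data cost

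*Protocol*

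**What the plan says.** Section 4.1.1 gives this definition: "The primary fMRI outcome will be change in amygdala BOLD response to emotional faces from baseline (prep, 1 day pre-DD1) to scan 2 at 6-weeks", counted from the first dosing day. The arms are then compared as "Change after psilocybin (condition 1) vs change after escitalopram (condition 2". No test, model or covariate is named.

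Section 1.1 confirms that both scans are part of the design ("we will use functional magnetic resonance imaging (fMRI) at baseline and six weeks after the initial dosing session") and gives the prediction in the same change form: "responses to emotional faces after-versus-before treatment will be greater in condition 1 (psilocybin) than in condition 2 (escitalopram".

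Three other places bear on how the contrast would be analysed:

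- Section 4.1.2 uses the same change-versus-change sentence for the QIDS. Section 10 attaches a test to that outcome: "The study is powered for a baseline vs week 6 t-test on the QIDS-16 (condition 1 vs condition 2". Section 10 says nothing about the analysis of the fMRI outcome.
- Section 2.3.3 names a baseline covariate for regression: "Prior attitudes to treatments will be collected at baseline and entered into regression analyses". Baseline amygdala response is not named there or elsewhere.
- Section 4.2.1 supports the sample size for imaging in words only ("These are appropriate numbers for the imaging"). It gives no effect size, standard deviation, scan-to-scan correlation or power for the amygdala response.

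**The concern.** On the natural reading, the baseline scan enters the primary fMRI result only by subtraction. The only test that the protocol attaches to this form of contrast is the t-test for the QIDS, which is unadjusted.

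Subtracting a noisy baseline with a fixed weight of one puts more baseline noise into the outcome than is needed. A linear model estimates the weight from the data and so removes that excess.

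Section 1.1 calls a different mechanism of action crucial, and this contrast is its primary test. It rests on about 30 patients per arm with no imaging power calculation, so precision should not be given up when the data to recover it are already collected.

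**Working it through.** **The plan's own figure.** There is no computed sample size or power for the fMRI outcome. The only calculation is for the QIDS: "we would require 20 patients per condition to achieve the desired power of 80%, p < 0.05". With SD 5.6 and a difference of 9.2 − 4.7 = 4.5, a one-sided 0.05 test gives 20 per arm; a two-sided test gives 25 (26 with the t distribution). The figure therefore reproduces only one-sided. It does not bear on the present point, because it concerns another outcome.

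**Inputs.**
- n = 30 per arm, from section 4.2.1.
- Two-sided 5% level: assumed, because sidedness is not stated.
- Equal single-scan variance s² at both scans and a common slope in both arms: assumed.
- rho, the correlation between baseline and week-6 amygdala response: not in the protocol, so shown from 0.2 to 0.9.
- 80% power for the plain change score: a reference point chosen to make the comparison readable, not a figure from the protocol.

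**Variances.**
- Change score: Var = s² + s² − 2·rho·s² = 2s²(1 − rho).
- Baseline-adjusted: Var = s²(1 − rho²).
- Ratio, adjusted to change: (1 − rho²) / [2(1 − rho)] = (1 + rho)/2, which is below 1 for every rho below 1.

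**Power.** With 30 per arm, the change-score t-test has 80% power at a difference of 0.736 SD of change. Adjustment divides the SD by the square root of 2/(1 + rho), so the effect in SD units becomes 0.736 / √((1 + rho)/2). At rho 0.5 this is 0.736 / 0.866 = 0.850.

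| rho | Variance ratio | Fall in SE | Change-score n per arm matching 30 adjusted | Power, change score | Power, adjusted |
|---|---|---|---|---|---|
| 0.2 | 0.60 | 22.5% | 50 | 80% | 95% |
| 0.3 | 0.65 | 19.4% | 46 | 80% | 93.5% |
| 0.5 | 0.75 | 13.4% | 40 | 80% | 90% |
| 0.7 | 0.85 | 7.8% | 35 | 80% | 86% |
| 0.8 | 0.90 | 5.1% | 33 | 80% | 84% |
| 0.9 | 0.95 | 2.5% | 32 | 80% | 82% |

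The matching n is 30 divided by the variance ratio; at rho 0.5 it is 30 / 0.75 = 40.

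**Cost of the covariate.** The last column ignores the degree of freedom and the small variance cost of estimating the slope. Charging both lowers each figure by less than one point, to about 95%, 93%, 89%, 85%, 83% and 81%. The net gain thus runs from about 15 points at rho 0.2 to about 1 point at rho 0.9.

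**A marker for low rho.** The variance of the week-6 scan alone is s². It is smaller than 2s²(1 − rho) when rho is below 0.5. In that range a plain change score is less precise than ignoring the baseline scan altogether; the adjusted model is never in that position in large samples.

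**The case against.** The strongest case against is that section 4.1.1 names an endpoint and the arms to compare, and stops there. A linear model of change with baseline as a covariate gives the same treatment estimate and standard error as a model of the week-6 value with that covariate, and it fits the section's wording without altering a word. Section 2.3.3 shows that baseline variables may enter regressions. Covariate lists are commonly left to the statistical analysis plan. All of this stands. A reader might infer that the protocol has committed the trial to an unadjusted change score; it has not, because no passage chooses an estimator or excludes adjustment.

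It also stands that the loss is one of precision only. A reader might infer bias from chance imbalance at baseline and regression to the mean. Under randomisation the change-score contrast is unbiased on average, and the shift caused by a chance imbalance is the same loss of precision seen from another side, not a second harm.

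Finally, the size cannot be fixed. A reader might take the gain to be at least five points whatever rho is, but that holds only up to about rho 0.7. The lack of an imaging power calculation is a separate matter, which adjustment does not cure.

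What survives is narrower. Read literally, and in line with the t-test named for the identically worded QIDS contrast, the text leads to the less precise analysis. A better one is available from data already in the design.

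**Conclusion.** The point holds as an improvement in precision, not as an error of validity. A plain comparison of change scores would be unbiased, with a variance 2/(1 + rho) times that of the baseline-adjusted comparison. For a contrast with 80% power at 30 per arm, adjustment would raise power to about 90% at rho 0.5, with a range from 95% at rho 0.2 to 82% at rho 0.9 before the covariate's cost of under one point.

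These figures rest on equal variances at the two scans, a common slope, and an assumed rho and reference power that the protocol does not supply. The benefit is material at low to moderate scan-to-scan correlation and slight if the correlation is high. If the statistical analysis plan already names baseline amygdala response as a covariate, nothing remains to be done beyond aligning the protocol wording.

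**What to change.** Keep the endpoint in section 4.1.1 as it is and add one sentence: the between-arm difference in change in amygdala response (equivalently, in week-6 response) is estimated in a linear model with treatment arm and the patient's baseline amygdala response as covariates. State that this is the primary fMRI analysis, so that the choice between adjusted and unadjusted results is settled before the data are seen.

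The cost is one degree of freedom. No new data, visits or patients are needed.

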#### 4.1.2. Primary efficacy outcome measure and endpoint

Change in QIDS score from baseline (screening) to 6 weeks post initial dosing session (primary endpoint). Change after psilocybin (condition 1) vs change after escitalopram (condition 2). The criteria for determining response will be a reduction of 50% in the QIDS scores and remission will be scores of  $\leq 5$  on the QIDS, as per convention [12].

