#### 2.5 Procedures

The patient's immediate care team will be made aware of the study and will identify a patient and ask them if they are willing to be contacted by us. The primary caregiver will then inform us of any patients who are interested in participating and provide a contact telephone number and/or email. The patient will be issued with an A4 summary sheet containing a brief summary of the study and our contact details. The more comprehensive information sheet will also be made available to them. After the patient has initiated contact with us, we will inform them of the nature of the study and organise an appropriate time for an initial telephone screen. We will ask the patient if we can contact their GP/psychiatrist and this will be done via an email using a standard letter template.

Eligibility will be principally determined by the study psychiatrist who will thoroughly screen all patients to identify and confirm the presence of major depression and exclude other conditions. Supporting information from relevant mental health professionals and/or general practitioners will be sought prior to entry into the trial to confirm diagnosis and ensure that all patients meet the inclusion criteria.

If the patient appears to be eligible (post-telephone screen and post-contact with their GP/psychiatrist), a date for the first screening visit will be arranged. This will be a meeting with the study psychiatrist to review patient history, current symptoms, and to further check inclusion and exclusion criteria.

There will be around 4 weeks from first screening visit to the first study day visit to allow analysis of screening data (e.g. blood tests) to determine eligibility and enable contact to be made between their GP and/or mental health practitioners, and so that proper and cautious washout of antidepressant (4 weeks for fluoxetine and 2 weeks for other antidepressants) can be done, where applicable. If no medication washout is required, the time from screening to study day one can be shorter than 4 weeks, although we will strive to acquire weekly QIDS ratings as soon as the patient's entry into the trial is confirmed. In cases where medication washout is required, if symptoms show a marked increase in relation to the cessation/tapering

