of medications, we will discuss with the patient and their GP or mental health caregiver whether the patient should withdraw from the trial so that previous medications can be resumed or new ones given. There will be ~7 weeks from the first (post-screening) study visit (**visit 2, scan 1**) to the primary end point/blind broken (**visit 7**), after which patients may return to their normal treatments if they so wish.

Patients will be required to make **7 visits** (see fig. 2). Patients will be assessed for up to six months after the initial dosing session; however, the study blind will be broken 6 weeks after the dosing session. Treatment as normal can then take place after the study blind has been broken.

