## 2.6. Visits

## Visit 1: Screening

Screenings typically take up to **4.5 hours** and include a physical examination by the study doctor, an ECG, and a period of MRI scanner acclimatisation, i.e. the patient will be invited to spend a period lying in an MRI scanner to assess whether they can tolerate the environment/conditions. Consent to enter the study will be sought from each participant after a full explanation has been given, the study information sheet has been issued and time allowed for consideration. Signed informed consent will be obtained for each patient.

We will know whether or not the patient is eligible for the trial ~3-days post screening (depending on receipt of relevant confirmation of diagnosis from the patient's GP or psychiatrist). As soon as eligibility is confirmed, the patient will be randomly allocated to one of the two study conditions.

If eligible, and if the patient wishes to participate in the trial, as soon as study entry is confirmed, a patient taking antidepressant medication will be required to begin coming off this medication, in a gradual, tapered fashion. We will ask that they inform their primary care giver of their decision to do this and we will manage medication withdrawal with their awareness. Medication withdrawal is typically done via gradual titration (e.g. halving of dose in first week) and the study psychiatrist will oversee this process in correspondence with the patient's GP and/or psychiatrist.

As soon as entry into the trial is confirmed, patients will be asked to complete the weekly QIDS-16 [12].. Patients will complete this up until the 6-week post dosing day, when the blind is broken. Use of the QIDS-16 [12] will enable us to track patient's mental health for the duration of the trial, facilitating patient monitoring and safety, while providing potentially useful data on weekly mood cycling pre versus post treatment [42].

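### In patients medicated at screening, the primary QIDS change starts from an on-drug score taken before washout; adjusting for the pre-dose QIDS-16 already scheduled is a cheap improvement on the named t-test

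*Protocol*

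**What the plan says.** - **Baseline.** Protocol section 4.1.2 sets the outcome as "Change in QIDS score from baseline (screening) to 6 weeks post initial dosing session (primary endpoint", compared between the two conditions.
- **Response.** The same paragraph adds: "The criteria for determining response will be a reduction of 50% in the QIDS scores". It names no separate reference score, so screening is the natural reading. Remission is a QIDS of 5 or below.
- **Randomisation.** Section 2.6, Visit 1: "As soon as eligibility is confirmed, the patient will be randomly allocated to one of the two study conditions". Eligibility is expected to be known about 3 days after screening.
- **Taper and washout.** Once entry is confirmed, "a patient taking antidepressant medication will be required to begin coming off this medication, in a gradual, tapered fashion". Section 2.5 leaves about 4 weeks between screening and the first study day so that "proper and cautious washout of antidepressant (4 weeks for fluoxetine and 2 weeks for other antidepressants) can be done".
- **Worsening.** Section 2.4.1 accepts that depression can worsen on withdrawal. Section 2.5 provides for it: "In cases where medication washout is required, if symptoms show a marked increase in relation to the cessation/tapering" of medication, the team discusses "whether the patient should withdraw from the trial so that previous medications can be resumed or new ones given".
- **QIDS between screening and dosing.** "As soon as entry into the trial is confirmed, patients will be asked to complete the weekly QIDS-16" (section 2.6). The Study Timeline table also lists QIDS at Visit 2, the day before first dosing.
- **Test.** Section 10 says the study is powered for a t-test of baseline against week 6 on the QIDS-16, between conditions.

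**The concern.** A medicated patient's baseline is measured on the old drug; treatment starts weeks later, off it. If QIDS rises during washout and some of the rise lasts to week 6, change from screening mixes the washout effect with the response to treatment. The mix differs between patients, because some are medicated and some are not.

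Two things are at stake. First, within-arm mean change and the proportion of responders will be read as what followed treatment, yet in medicated patients they start from a different state. Second, drift that varies between patients adds variance to a change-score t-test, although a score that could absorb it is already scheduled.

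**Working it through.** **Inputs from the protocol.** Change SD 5.6 (variance 31.36), reductions 9.2 and 4.7, 30 completers per arm (section 4.2.1). The 4.7 is printed as 9.2/2, which is 4.6; the planning difference is therefore 9.2 - 4.7 = 4.5.

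**The plan's own figure.** n = 2(z_alpha + z_beta)^2 x 31.36/4.5^2. One-sided 5%, 80% power: 2 x (1.645 + 0.842)^2 x 1.549 = 19.2, so 20 per arm, as stated. Two-sided 5% gives 25 (26 with the t distribution). The protocol does not state sidedness, and nothing below depends on it. At 30 per arm, two-sided, power at 4.5 points is 86.4% and the half-width is 2.002 x 5.6 x sqrt(2/30) = 2.89.

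**Assumptions not in the documents.** Share medicated p = 0.1 to 0.4; washout rise d = 2 to 4 points; fraction f of the rise still present at week 6 = 0 to 1. Let S be the screening score, P = S + D the pre-dose score and Y = Y0 + fD the week-6 score. D equals d with probability p and is otherwise 0, independently of S and Y0, and var(Y0 - S) = 31.36.

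**Between-arm difference.** S is measured before randomisation, so its expected difference between arms is zero and subtracting it cannot bias the comparison.

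**Within-arm change.** Improvement from S is understated by f x p x d. With p x d = 0.2 to 1.6, that is 0 at f = 0 and 0.2-1.6 points at f = 1. Improvement from P is overstated by (1 - f) x p x d: 0.2-1.6 at f = 0 and 0 at f = 1.

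**Noise in the t-test on change from S.** Variance = 31.36 + f^2 x p(1-p)d^2, where p(1-p)d^2 runs from 0.1 x 0.9 x 4 = 0.36 to 0.4 x 0.6 x 16 = 3.84.

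| f | half-width | power at 4.5 points |
|---|---|---|
| 0 | 2.89 | 86.4% |
| 0.5 | 2.90-2.94 | 85.4-86.3% |
| 1 | 2.91-3.07 | 82.3-86.1% |

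**ANCOVA.** Let r be the correlation of S with Y0 (assumed 0.3-0.5) and k = SD(S)/SD(Y0) (assumed 1, 0.7, 0.6). Then V0 = var(Y0) = 31.36/(1 + k^2 - 2rk). Because P - S = D, adjusting for both scores leaves V0(1 - r^2) at every f.
- Best case, k = 1, r = 0.3: V0 = 31.36/1.4 = 22.40; residual 22.40 x 0.91 = 20.38; half-width 2.33.
- Worst case, k = 0.6, r = 0.5: V0 = 31.36/0.76 = 41.26; residual 41.26 x 0.75 = 30.95; half-width 2.88.

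These are variance falls of 35% and 1%. Adjusting for screening alone gives V0(1 - r^2) + f^2 x p(1-p)d^2: 2.33-2.88 at f = 0 and 2.35-3.05 at f = 1. The pre-dose score therefore narrows the half-width by nothing at f = 0 and by 0.02-0.21 at f = 1. If it carries a further error of SD 2 (assumed), the two-score half-width at f = 1 is 2.35-2.96.

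**Response.** Changing the reference from S to P moves the cut-off by d/2 = 1 to 2 points. Simulation used an assumed mean screening QIDS of 16, SD 3 or 4, mean change 9.2 or 4.6, and f of 0 or 1. It reclassifies 4.8-15.5% of medicated patients. Multiplied by p, that is 0.5-6.2% of all patients; multiplied by 30, it is 0.1-1.9 patients per arm. A fixed remission cut-off does not move.

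**The case against.** **Screening is a defensible baseline.** Patients are randomised within days of it, and it is the only QIDS clearly scheduled before randomisation. The pre-dose score comes after randomisation, and patients who leave during washout may not have one. This stands, and is why screening should remain the reference.

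**The pre-dose score is not plainly better.** If the washout rise is transient, the pre-dose score is the inflated one and would flatter both arms. This stands too. A reader might infer that the pre-dose score should replace screening as the baseline. The documents do not support that, because they do not say how long a rise lasts.

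**The harm is small and rests on assumptions.** Section 2.3.3 prefers unmedicated patients, and possible withdrawal after a marked increase would limit drift among completers. The pilot behind the SD of 5.6 also used washout (section 2.4.1), so some drift may already be counted. All of this stands. Power drops below 80% only on a wider assumed grid: 78.5% at a 4.6-point difference with 60% medicated, a fully lasting 4-point rise and an SD of 3 in that rise.

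**Adjustment belongs in the SAP.** The SAP is not shown and may add covariates, so their absence from the protocol is not a fault in itself. The protocol does, however, fix the screening baseline and name only a t-test, and a clearly better analysis can be given.

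**Different fMRI baseline.** Section 4.1.1 starts the fMRI outcome from the day before dosing. This is no contradiction, since the first outcome scan takes place at that visit.

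**Conclusion.** The point holds in a limited form, as a cheap improvement of minor to moderate weight. For patients medicated at screening, the reference score is taken on drug, before taper and washout. The consequences are some avoidable noise and, in those patients, within-arm change and 50% response figures not referred to the state in which treatment began.

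A reader might infer that the primary comparison is biased. It is not: the reference is measured before randomisation, and remission uses a fixed cut-off. Nor do the documents show a serious loss of power. With 10-40% medicated and a 2-4 point rise, the half-width is at most 3.07 against 2.89, and power at 4.5 points is at least 82%. The true size, and the direction in which either reference misstates the treatment change, cannot be determined from the protocol.

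Adjusting for both scores gives 2.33-2.88 whatever share of the rise persists, provided the pre-dose score carries no further error. Most of that gain comes from adjustment itself.

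**What to change.** 1. Keep screening as the reference for change in section 4.1.2, and state that the 50% response rule uses it too.
2. In section 10 and the SAP, analyse week-6 QIDS by ANCOVA, or by a mixed model on the weekly QIDS-16. Adjust for the screening QIDS and the last standard weekly QIDS-16 before first dosing. Use the screening score where no later pre-dose score exists.
3. Report change and response from the pre-dose score as a sensitivity analysis.
4. State the downside: the pre-dose score is collected after randomisation, though blinded and before treatment.

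Two clarifications go with this. Section 2.2.1 attaches a daily version of the scale to the day before dosing, so say that the standard weekly QIDS-16 is completed at Visit 2 or within the preceding week. Section 4.2.3 omits QIDS from the screening list while the Study Timeline table shows it at Visit 1, so add it.

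The cost is protocol and SAP wording; no visit or instrument is added.
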